
Project design

This is a parallel multicentre randomized controlled trial. Women expecting their first child will be randomized to either having one midwife assisting the active phase of the second stage of labor and the birth of the baby (standard care) or to having two midwives present.

That means that if the woman is randomized to the intervention, the midwife responsible for the birth is assisting the woman as usual but asks a second midwife to be present in the birthing room ready to help her if necessary (intervention). The study is designed according to CONSORT statements (21).

The hypothesis in this study is that the collegial presence of another midwife during the second stage of labor will reduce perineal trauma grade III-IV (primary outcome).

Data from the National Birth Register show that 4.1% of first-time mothers suffered severe perineal trauma in Sweden 2017. The prevalence of severe perineal trauma varies between different regions in Sweden (3). To be able to detect a 50% reduction in severe perineal trauma grade III-IV from 4.1% to 2.0% with 80% power and a 95% level of significance, 1052 women in each group will be needed. The 50% reduction is based on regional figures after a change in practice and is therefore clinically significant. Allowing for a possible drop-out rate of 20% and another drop-out of 20% for possible cases of obstetric emergencies where another midwife will be needed regardless of randomization, this will result in 1473 women in each group and 2946 women in total.

The primary outcome is the prevalence of severe perineal tears grade III-IV.

Secondary outcomes are the prevalence of second-degree tears, vaginal tears, women's experiences of two midwives attending the birth and midwives' experiences of the intervention. Additional secondary outcomes regarding the woman are: the prevalence of episiotomy, first-degree tears, intact perineum (no tear), labial and periurethral tears, postpartum bleeding >500 ml, birth position, instrumental delivery, urinary incontinence, anal incontinence, symptoms of pelvic organ prolapse and sexual function after one year, and self-reported mental health one month and one year after birth. For the one-year follow-up the following validated questionnaires will be used: PFIQ7, PFDI-20, and FSFI and EPDS (22-24). Secondary outcomes regarding the newborn child are: Apgar scores at 1, 5 and 10 minutes, umbilical cord blood gases, and breastfeeding within two hours after birth.

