Inclusion criteria: Swedish speaking women expecting their first child or with a prior caesarean section opting for a vaginal birth, with a singleton live foetus in cephalic presentation from gestational week 37+0.

Participating clinics: The maternity ward at Karolinska University Hospital Huddinge and Solna, and the maternity wards at SUS Malmö and Lund. With four participating clinics the time for patient recruitment will be shortened and this will also increase the generalizability of the results.

Randomization process: It will not be possible to blind either women or midwives in this study. The participants will be randomly allocated (1:1) to the intervention group (collegial presence of another midwife during the second stage) or to the standard care group (one midwife is responsible for the care during the second stage). Randomization will take place at the start of the second stage. To allow for equal distribution between the groups, block randomization in blocks of ten will be used. The midwife in charge will be responsible for the randomization process. Sealed and opaque envelopes will be used and will be prepared with a unique code consisting of a first code letter identifying each study site, a second code letter identifying which group it belonged to (intervention or control) followed by a consecutive number.

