Data collection: After the birth the tear will be diagnosed together with a midwife or an obstetrician who has not been involved in the birth. Tears will be sutured according to the guidelines at each participating study site. The midwife responsible for the birth will complete a questionnaire which will contain questions regarding the woman; labor and birth variables, methods of preventing perineal trauma, questions regarding the newborn, diagnosis of the tear and how the tear was sutured. If a second midwife has been present during the second stage (intervention) the responsible midwife (midwife no 1) will also complete questions on the assistance she got from the second midwife and how this assistance was experienced. Data will also be retrieved from the participating women's records by using the local database of each study site (Obstetrix). When the intervention has taken place the second midwife will also complete a questionnaire. This questionnaire will contain questions on what assistance she gave the midwife responsible for the woman (if any) and how she experienced being present during the second stage of labor. The questionnaires completed by the midwives will be coded with the same code as the participating woman received when she was allocated to the intervention or standard care.

The questionnaire regarding women's experiences of the intervention or standard care and the methods used to prevent perineal trauma will be sent by email one month after the birth. The questions in the questionnaire are study specific, containing questions regarding the experience of the second stage of labour, preventive methods used, initiation of breastfeeding, perineal pain, pain medication used, and resumption of sexual intercourse. In addition the Edinburgh postnatal depression scale (EPDS) will be used to assess mental health (23). The follow-up with validated questionnaires regarding pelvic floor symptoms will be sent to the women one year after birth. For the one year follow-up, the questionnaires used are Pelvic floor impact questionnaire (PFIQ7), Pelvic floor distress inventory (PFDI-20), the Female Sexual Function Index (FSFI) and Edinburgh postnatal depression scale (EPDS)

(22, 23, 25). If the woman does not complete the questionnaire in two weeks, she will be reminded, and the questionnaire will be sent by mail.

Analysis

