Descriptive statistics will be used to present the data. The means, SD, median, quartiles, and 95% CI will be calculated when appropriate as will frequency tables, stratified by the two arms. The primary statistical analysis is intention to treat but a per protocol analysis will also be performed. For comparison between the two groups, t-tests will be used for continuous variables and Chi-square tests for dichotomous variables. A possible preventive effect of having two midwives attending the second stage of labour and birth of the baby will be calculated as a relative risk of severe perineal trauma (tear grade III-IV) with 95% CI. We will adjust for study site using logistic regression. If baseline variables are not balanced by randomisation we will adjust for those using multivariate logistic regression. Response analyses regarding primary outcome will be undertaken at each study centre. Secondary outcomes will be compared using t-tests for continuous variables and Chi-square tests for dichotomous variables. The Mann-Whitney U-test will be used for outcomes based on scores. The project has access to a statistician from Clinical Studies Sweden, Forum South.

Adverse events

As approximately 50% of the maternity wards in Sweden already have implemented the clinical practice with two midwives without reporting any adverse side-effects, such as increased rates of severe perineal trauma or an increase in Apgar scores <4 at five minutes, we will not perform routine interim analyses throughout the data collection. Analyses will be performed if the maternity wards notice a negative trend in outcomes related to the mother (severe perineal trauma, postpartum haemorrhage >1000 ml) or the baby (Apgar scores and neonatal resuscitation).

Clinical significance

The number of women seeking care for pelvic floor problems related to childbirth is increasing. Improving the health and well-being for women giving birth is important on a personal level but also for society. There is an ongoing debate in the Swedish media and among women regarding severe perineal trauma. Childbirth organizations are upset that care providers are not able to prevent injuries and find it extraordinary that gaps in our knowledge still exist in this field of research. Many women are afraid of giving birth vaginally because they fear an extensive tear and the consequences such a tear might have on their

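### Site adjustment appears to stop at the primary outcome, while the tests named for secondary outcomes leave site out: a small loss of precision that a wording change would recover

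*Protocol*

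**What the plan says.** In the protocol's Analysis section, the preventive effect on grade III-IV tears is to be given as a relative risk with 95% CI. The next sentence announces adjustment for study site by logistic regression and names no outcome. Site-level analyses of the primary outcome follow. Secondary outcomes then get their own rule: "Secondary outcomes will be compared using t-tests for continuous variables and Chi-square tests for dichotomous variables". Outcomes based on scores get the Mann-Whitney U-test. No site term or stratum is mentioned for any of them.

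Three other places bear on site:

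- **Project design, Randomization process.** Allocation is 1:1 in blocks of ten, from envelopes whose code has "a first code letter identifying each study site", then a group letter and a consecutive number. Stratification by site is not stated in words.
- **Project design, Data collection.** "Tears will be sutured according to the guidelines at each participating study site".
- **Project design, sample size paragraph.** Severe perineal trauma is said to vary in prevalence between Swedish regions. Nothing comparable is said of other tears.

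**The concern.** The authors treat site as worth adjusting for once, then name tests for the secondary outcomes that cannot include it. Several specific aims rest on those outcomes: vaginal tears, grade II tears and pelvic floor symptoms at one year. Because the protocol names the tests, this is a choice it makes and not a detail left open.

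Three things are at stake. First, if envelopes were blocked within site, a test that ignores site uses a standard error slightly too large for the design and gives away some precision. Second, primary and secondary results would be analysed on different footings without a stated reason. Third, the one-month and one-year outcomes come from questionnaires. Balance by site at randomisation need not persist among responders, and an unstratified comparison has no protection against that.

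**Working it through.** **The plan's own figure.** The only sample size calculation concerns the primary outcome: "from 4.1% to 2.0% with 80% power and a 95% level of significance, 1052 women in each group will be needed". With pooled variance, two-sided 5% and mean rate 0.0305:

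n = [1.960 × √(2 × 0.0305 × 0.9695) + 0.842 × √(0.041 × 0.959 + 0.020 × 0.980)]² / 0.021² = 1051.4, rounded up to 1052.

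It reproduces. It does not bear on this point, since no secondary outcome has a power target.

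**Inputs for the check.** From the document: four clinics, 1:1 allocation, 2946 women in total, and a second-degree tear rate of 78% in primiparous women (Background). Assumed, because the document gives no site rates: equal site sizes and three sets of site rates averaging 78%.

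**Case A: blocks within site.** Let R² = variance of site rates / (0.78 × 0.22 = 0.1716), and k = 1 − R². The unstratified statistic then has true variance k where the test assumes 1.

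- True two-sided size = 2 × P(Z > 1.960/√k).
- Power of the unstratified test where the site-adjusted test has 80% = Φ(2.802 − 1.960/√k), with 2.802 = 1.960 + 0.842.

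| Assumed site rates (%) | Variance | R² | k | True size | Power |
|---|---|---|---|---|---|
| 75, 77, 79, 81 | 0.00050 | 0.0029 | 0.9971 | 0.0497 | 79.9% |
| 70, 75, 81, 86 | 0.00365 | 0.0213 | 0.9787 | 0.0476 | 79.4% |
| 63, 73, 83, 93 | 0.01250 | 0.0728 | 0.9272 | 0.0418 | 77.8% |

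A simulation with four sites, 368 women per arm per site and 40,000 runs agrees. Under no effect, chi-square rejected at 0.051, 0.048 and 0.042, and Mantel-Haenszel at 0.051, 0.050 and 0.049 (Monte Carlo standard error about 0.001). With a 4.5-point effect, power was 81.8% v 81.8%, 81.7% v 82.1% and 82.1% v 83.9%.

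For continuous outcomes the same formulas apply with k = 1 − ICC. An assumed site ICC of 0.01 gives size 0.0489 and power 79.7%. An ICC of 0.10 gives 0.0388 and 76.9%.

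**Case B: blocks not within site.** The unstratified test now has its nominal size, and the cost is precision alone. Power where the adjusted test has 80% = Φ(2.802 × √k − 1.960), which is 79.9%, 79.2% and 77.0% for the three spreads. Adjustment would also correct chance site imbalance between arms.

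**Non-response illustration (all values assumed).** Take two equal groups of sites with symptom rates of 30% and 20% and no treatment effect. Response is 70% and 50% in one arm, 60% and 60% in the other.

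- First site group's share of responders: 0.70/(0.70 + 0.50) = 0.583 in one arm, 0.50 in the other.
- Observed rates: 0.583 × 30 + 0.417 × 20 = 25.8% v 25.0%, a spurious gap of 0.83 points.
- Responders per arm: 0.60 × 1473 ≈ 884. Standard error: √[(0.258 × 0.742 + 0.25 × 0.75)/884] ≈ 2.1 points. The gap is about 0.4 standard errors.

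Stratifying by site removes this gap, because response was made to depend on arm and site alone.

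**The case against.** The strongest reply is that nothing here is an error. Unadjusted tests of secondary outcomes are valid under 1:1 randomisation, any departure from nominal size is in the cautious direction, and the losses are small unless sites differ greatly. All of that stands, and it sets the size of the point.

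Other parts of the reply limit what may be inferred:

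- **Adjustment for the primary outcome only.** A reader might take this as stated. The sentence names no outcome; its position and the separate secondary-outcome sentences suggest the restriction. If adjustment was meant for every outcome, the named tests still do not deliver it, so the wording needs attention either way.
- **Stratified randomisation.** A reader might take the site letter as proof. It implies site-specific lists, but the protocol never says so, and the reduced test sizes in Case A depend on it.
- **Tear rates differing by site.** The regional variation reported is for severe trauma only, the outcome for which adjustment is already planned. The clinics also belong to two hospital organisations, so regional variation does not show four different site rates.
- **Local suturing guidelines.** Suturing follows diagnosis and cannot predict grade II or vaginal tears. It bears on later pain, pelvic floor symptoms and sexual function.
- **Non-response.** No arm-by-site response pattern is documented, and selective response by symptoms would be untouched by a site term.

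It can also be said that adjusted models may follow in a statistical analysis plan. They may, but the protocol already names the tests, and a plan that followed it would leave site out.

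**Conclusion.** The point holds as a minor one. The protocol appears to adjust only the primary outcome for site and names secondary tests that leave site out, without giving a reason. If allocation was blocked within site, those tests are slightly conservative: about 0 to 2 points of power for binary outcomes under the assumed spreads, and about 3 points for a continuous outcome at an assumed ICC of 0.10. If it was not, they are valid but less precise than they could be.

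A reader might conclude that the secondary tests give false positives or biased estimates. The documents do not support that: with balanced allocation there is no type I error inflation and no bias by site. Bias through site can arise only among questionnaire responders, and only under a response pattern that is assumed here. All sizes rest on assumed site rates, ICCs and response rates.

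**What to change.** Replace the secondary-outcome wording in Analysis with a statement that these outcomes, too, are analysed with site as a stratum or covariate. For example:

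- binary outcomes: Mantel-Haenszel relative risk with the Cochran-Mantel-Haenszel test;
- continuous outcomes: a linear model with arm and site;
- scores: the van Elteren test, which is the site-stratified Wilcoxon test.

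In the same edit, name the outcomes that the existing site-adjustment sentence covers, and state under Randomization process whether the blocks of ten were formed within site.

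The cost is wording only. Site is already the first letter of every participant code, so no new data are needed. With four sites and 2946 women planned, the strata are large enough for common outcomes.
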